# **11.3.** Events exempt from reporting as AE/SAEs

Hospitalisation for a pre-existing condition, including elective procedures planned prior to study entry, which has not worsened, does not constitute a reportable serious adverse event; e.g., hospitalisation for procedures and treatments specified within the protocol, and standard supportive care for the disease under study are not reportable SAEs, and do not require SAE reporting.

## **11.4.** Reporting complications in relation to surgery

Any complications related directly to breast surgery and not considered related to AI treatment (example: prolonged hospitalisation, infection etc.) will not be part of the safety reporting but will be collected in the relevant trial CRF. These will be assessed using the Clavien-Dindo Classification of surgical complications.

## 11.5. Reporting side effects in relation to IMP treatment

Side effects frequently experienced by patients undergoing AI therapy for breast cancer are collected as outcomes in the trial's CRF for the duration of patient participation in the trial (15-months for both arms) and include the following:

- Vasomotor including hot flashes/flushes and night sweats/hyperhidrosis
- Musculoskeletal including myalgia and arthralgia/joint pain;
- Central nervous system including nausea, vomiting, and fatigue;
- Urogenital including vaginal haemorrhage/bleeding, vaginal dryness and urinary tract infection;
- Gastrointestinal including anorexia;
- Other including alopecia.

Generally, these are mainly mild or moderate in nature, and most are associated with oestrogen deprivation.

The above events must also be reported as SAEs if they meet the definition of serious and occur during the trial's defined safety reporting window.

## 11.6. Assessment of Causality

The relationship of each serious adverse event to the trial medication must be determined by a medically qualified individual according to the following definitions:

	Attribution (Causality)	Description	
Non-related	Unrelated	The AE is clearly NOT related to the intervention	
	Unlikely	The AE is doubtfully related to the intervention	
Related	Possibly	The AE may be related to the intervention	
	Probably	The AE is likely related to the intervention	
	Definitely	The AE is clearly related to the intervention	

## 11.7. Severity grading

Severity of events in this trial will be assessed based on the most recently published Common Terminology					
Criteria	for	Adverse	Events	(CTCAE)	scale
(https://ctep.cance	r.gov/protocolde	velopment/electronic	_applications/docs/	CTCAE_v5_Quick_Refe	erenc

EndoNET\_Protocol\_V4.0\_21Aug2024

© Copyright: The University of Oxford and Oxford University Hospitals NHS Foundation Trust 2022 Page 60 of 84

e\_5x7.pdf). AEs will be rated according to these grades: 1 = mild, 2 = moderate, 3 = severe or medically significant, 4 = life-threatening and 5 = death related to AE.

## 11.8. Safety reporting window

The safety reporting window is defined as the time the AI is given in the pre-surgical (neoadjuvant) period for the trial in both arms (between patient consent and the surgery: target of 2-4 weeks (up to 8 weeks permitted for trial purposes) in the control arm, and 6 months (+/- 1 month) in the NET arm). The justification of the chosen safety window is based on the use of adjuvant AI post-surgery as the current SoC where the AI is no longer classified as an IMP.

## **11.9.** Reporting Adverse Events and SAEs including reporting period

All side effects collected as outcomes in the CRF that also meet the definition of serious will need to be reported as an SAE during the trial's safety reporting window. All other SAEs considered related to the AI treatment should also be reported on an SAE form. Reporting must be within 24 hours of the site being aware of the SAE. Once a SAE is entered in the database, this automatically triggers a notification to the CTU.

The following information will be reported on the SAE form: relevant brief medical history, description of event (i.e. diagnosis term), date of onset and end date, severity, assessment of relatedness to trial medication, or drug–to drug interaction if participant is taking concomitant drugs; reason for seriousness, and action/s taken to deal with the event. SAEs will be closed following resolution. Follow-up information should be provided as necessary.

In the event that the clinical database is not available for reporting of SAEs within 24 hours, sites must complete a paper SAE Form and email it to the trial inbox email account: [contact].

## **11.10.** CTU Review of reported SAEs

On notification/receipt of a SAE, the Trial Management Team at the CTU will perform an initial check of the report and request any additional information from the site team. The SAE will also be reviewed by a Nominated Person for the trial.

## 11.11. Assessment of Expectedness

For SAEs that require reporting, expectedness of SARs will be determined according to the section 4.8 of the Summary of Product Characteristics of the relevant IMP Letrozole, anastrozole and or exemestane. The nominated SmPCs for each of the trial AIs is Femara (letrozole), Arimidex (anastrozole) and Aromasin (exemestane). The RSI used (within the SmPC) will be the current Sponsor and MHRA approved version at the time of the event occurrence, even for any follow-up information of the same event. If an event is deemed to be either more severe or specific in nature than what is listed in the RSI used then it may be considered as unexpected.

This assessment will be performed by the Nominated Person for the trial in the CTU.

EndoNET\_Protocol\_V4.0\_21Aug2024

© Copyright: The University of Oxford and Oxford University Hospitals NHS Foundation Trust 2022 Page 61 of 84

# 11.12. SUSAR Reporting

## 11.12.1. Reporting to the MHRA/REC

All SUSARs will be reported by the CTU (sponsor delegate) to the MHRA and to the REC and other parties as applicable. For fatal and life-threatening SUSARS, this will be done no later than 7 calendar days after the Sponsor or delegate is first aware of the reaction. Any additional relevant information will be reported within 8 calendar days of the initial report. All other SUSARs will be reported within 15 calendar days.

## **11.12.2.** Reporting SUSARs to the PIs

PIs will be informed of all SUSARs that occur in the trial reporting period at the same time that the MHRA/REC are being informed.

## 11.13. Development Safety Update Reports (DSUR)

The CI will submit (in addition to the expedited reporting above) DSURs once a year throughout the clinical trial, or on request, to the MHRA, Ethics Committee, HRA (where required) and Sponsor. The DSUR will only be sent to sites, on request.

As the trial is a Type A trial under the MHRA notification scheme, the HRA Annual Progress Report (APR) form will be used as a template for the DSUR. The cover letter will state that this is an APR in lieu of a full DSUR, and include the EudraCT number and CTA reference number.

For assessment of SARs in the DSUR, the RSI that was approved at the **start of the DSUR safety reporting period** will be used for assessment of expectedness, as per OCTRU's SOP on DSUR. The date of the CTA authorisation will be the start of the safety reporting period of the trial.

# **12. STATISTICS (Main Trial)**

## 12.1 Statistical Analysis Plan (SAP)

The statistical aspects of the study are summarised here with details fully described in a pre-specified statistical analysis plan (SAP) that will be finalised prior to the final analysis data lock, or any planned interim comparative analyses. The SAP will be written by the Trial Statistician in accordance with the current OCTRU SOPs and will be finalised and agreed by the Trial Statistician, the CI and the TMG.

## **12.2** Description of Statistical Methods

Results will be reported in line with the CONSORT statement and relevant extensions (101, 104, 105).

All outcomes will be summarised using descriptive statistics overall and, when collected for both arms, split by treatment groups. Binary and categorical data will be summarised by frequencies and percentages. Continuous data will be summarised by means and standard deviations (SDs), or median and inter-quartile range if data are skewed. Corresponding 95% confidence intervals will be presented where possible. Visual representation of outcomes will be considered and, where it will support interpretation, presented.

EndoNET\_Protocol\_V4.0\_21Aug2024

© Copyright: The University of Oxford and Oxford University Hospitals NHS Foundation Trust 2022 Page 62 of 84 The primary analyses will be performed according to the intention-to-treat principle. Additionally, a per protocol analysis will be considered to examine the robustness of the primary analysis under the intention-to-treat principle.

The primary endpoint, rates of breast conserving surgery, will be compared between the two arms using a mixed effects logistic regression model, adjusting for treatment and clinical stratification factors as fixed effects and centre as a random effect. Additionally, a sensitivity analysis will be conducted that adjusts for other important prognostic factors.

Secondary endpoints, measured in both treatment groups, will be analysed comparatively as far as practically possible. Statistical methods used for comparison will depend on the outcome type and full details will be included in the SAP. QoL will be compared using a mixed effects linear regression model. The model will include treatment, baseline score and clinical stratification factors as fixed effects, centre will be included as a random effect. When QoL is assessed at additional time points between baseline and 15 months, time-by-treatment interactions will be incorporated as fixed effects and patient as a random effect. Mean scores and standard deviations will be plotted over time for visual representation. The predictive ability of Ki67 will be explored using logistic regression models. Time-to-event endpoints will be analysed using Kaplan-Meier curves, log rank tests, and Cox proportional hazards models or, in the presence of competing risks, by using cumulative incidence plots and Fine and Gray survival regression models. Continuous clinical endpoints will be compared using a two-group t-test and the difference in means will be presented with a 95% confidence interval. Binary clinical endpoints will be compared using a chi-squared test and the effect estimate reported in terms of the relative risk and 95% confidence interval. Ordinal clinical endpoints will be compared using a chi-squared test for trend. Multilevel regression models, with adjustment for stratification factors in line with the primary endpoint analyses, will be applied to secondary endpoints where it is both practical to do so and there are sufficient events to support this approach.

The primary analysis is planned in the final six months of the study period, at which point all participants will have completed at least 15 months of follow-up.

It is anticipated that all statistical analysis will be undertaken using Stata (StataCorp LP, www.stata.com) or other well validated statistical package.

\* **Note:** From Protocol 4.0, FACT-B +4/ES will no longer be collected at 7 and 12 months (see Appendix 1). Data collected on patients up until this timepoint will be reported descriptively and will not be included in formal comparisons due to low numbers in comparison with the overall sample size. The SAP will provide further detail.

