## 6. OBJECTIVES AND OUTCOME MEASURES

#### **6.1 HYPOTHESIS:**

Neoadjuvant endocrine therapy (NET) reduces breast cancer size prior to surgery, reducing surgical burden resulting in a higher proportion of patients treated with breast conservation surgery (BCS).

RESEARCH QUESTION: In post-menopausal women with ≥15mm, strongly ER+, invasive breast cancer, where chemotherapy or anti-HER-2 therapy is not planned, does NET increase the proportion of patients who have BCS by 15 months post-randomisation?

	Objectives	Outcome Measures	Timepoints
Primary	The overall aim is to evaluate whether 6 (+/- 1) months of NET reduces surgical burden resulting in a higher proportion of breast conservation in post- menopausal women with ≥15mm, strongly ER+ breast cancer who are not planned or have not started chemotherapy or anti- HER-2 therapy 	Proportion of patients who have breast conservation (surgery)	15 months post- randomisation
Secondary	
 
To evaluate whether 6 months of NET results in better HRQoL over 15 months
 
	
 
Difference in global HRQoL (as measured by FACT-B)
 
	
 
Baseline, 6 weeks or post-operative, 5 and 15 months post- randomisation
 

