## 9.6. Randomisation (Main Trial)

We will randomise eligible patients using the centralised validated computer randomisation program through a secure (encrypted) web-based service, RRAMP (https://rramp.octru.ox.ac.uk), provided by the Oxford Clinical Trials Research Unit (OCTRU), accessed via the study's REDCap instance, with a minimisation algorithm to ensure balanced allocation across treatment arms, stratified in a 1:1 ratio to either NET followed by standard of care or standard of care using:

- Age group (<60, 60-70, 70+ years);
- Nodal status (N0 vs N1 or N2);
- Recruiting centre, and
- Surgical indication at baseline (BCS vs mastectomy)

To ensure the unpredictability of treatment allocation the minimisation algorithm will include a probabilistic element and a small number of participants randomised by simple randomisation. Stratification by centre will help to ensure that any centre-effect will be equally distributed in the trial arms and enable practical issues associated with the active intervention to be overcome. In the unlikely event that the randomisation system is down for any reason, if delays in randomisation occur to such an extent that they impact treatment planning felt to affect the prognosis of the participant, then they will be withdrawn and returned to the usual standard of care pathway if deemed necessary by the treating clinician. For participants who do not wish to or who are unable to comply with their randomisation outcome (according to the investigator and/or clinical team), they will continue to participate in the study but will be analysed on an intention to treat basis.

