## 9.9. Trial imaging (Main Trial)

## 9.9.1. Imaging for trial purposes

USS +/- breast MRI, are used in most centres to monitor response to preoperative neo-adjuvant treatment. In the NET arm USS is required 2-4 weeks after start of treatment in order to place the marker clip and take core biopsies for Ki67 measurements. USS is then required at 3 and 5 months to evaluate any possible tumour response to the AI. If a patient has dense breasts or a discrepancy between mammography and USS size estimates a baseline MRI is undertaken to assess disease extent. If local policy, the participant may have MRI at the follow up timepoints (e.g. at 3 and/or 5 months) to correspond to the USS evaluation. If breast MRI is standard practice for neo-adjuvant treatment at a centre then this may be used in this trial, in addition to USS.

Baseline USS examination should include examination of the whole breast to assess disease extent. The tumour is measured in at least two dimensions (usually perpendicular to each other) and documented in millimetres with the accurate position of the probe recorded and images archived to improve interobserver accuracy. In line with standard practice, the maximum tumour diameter will be recorded and used to assess tumour response using RECIST 1.1 criteria (102). It is advised that for the 3 and 5 month USS in the NET arm, that the radiologist should review any previous image(s) in order to try and replicate the same measurement planes to minimise the subjective bias in USS. It is also recommended that USS images are captured in both planes. This will also allow for use in future research.

The axilla should be assessed carefully prior to entry to the trial by USS (as per national guidelines for all patients with invasive breast cancer) with any abnormal nodes biopsied by core biopsy or fine needle aspiration cytology (FNAC). The number of abnormal nodes should be recorded and documented. USS guided core biopsy and marker clip insertion is undertaken at 2-4 weeks. Prior to biopsy the tumour size is measured taking care to use the same positioning as the baseline examination.

EndoNET\_Protocol\_V4.0\_21Aug2024

© Copyright: The University of Oxford and Oxford University Hospitals NHS Foundation Trust 2022 Page 48 of 84 MRI examinations if undertaken should follow local protocol.

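### Primary BCS model could add baseline ultrasound tumour diameter: a modest efficiency gain from data already collected, not an error in the plan

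*Protocol*

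**What the plan says.** Section 12.2 sets the primary comparison of BCS rates as a mixed-effects logistic regression, "adjusting for treatment and clinical stratification factors as fixed effects and centre as a random effect". Section 9.6 lists the minimisation factors: age group, nodal status, recruiting centre and the operation planned at entry ("Surgical indication at baseline (BCS vs mastectomy"). Tumour size is not on that list, so it is not in the primary model.

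Section 12.2 then provides for further adjustment outside the primary analysis: "a sensitivity analysis will be conducted that adjusts for other important prognostic factors". The factors are not named there.

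The measurement is available. Section 9.9.1 states that "the maximum tumour diameter will be recorded and used to assess tumour response using RECIST 1.1 criteria", and section 9.9.2 says the same for standard-of-care imaging, so baseline diameter is documented in both arms. Section 8.2.1 requires a tumour of at least 15 mm and a lesion visible on ultrasound, so the value should be close to complete.

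The hypothesis in section 6.1 runs through size: neoadjuvant endocrine therapy "reduces breast cancer size prior to surgery, reducing surgical burden resulting in a higher proportion of patients treated with breast conservation surgery".

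**The concern.** In a logistic model, leaving out a baseline variable that predicts the outcome costs some precision on the treatment effect. Size is a natural candidate here. The trial's mechanism is tumour shrinkage, and the protocol ties its 45% mastectomy rate to tumours above 2 cm (sections 5 and 12.3). Entry starts at 15 mm with no stated upper limit in millimetres; cT4 disease is excluded.

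The model already contains the planned operation, which reflects size to a large extent. It is only a yes/no variable, though. Among women indicated for mastectomy, starting diameter plausibly affects whether shrinkage allows conversion. Among women indicated for BCS, it plausibly affects whether re-excision ends in mastectomy, a sequence that section 5.2 anticipates for a few women.

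What is at stake is efficiency. A sensitivity analysis that includes size does not carry the primary p-value, so any precision it gains does not reach the primary test.

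**Working it through.** **1. The plan's own sample size.** Inputs from section 12.3: BCS 55% v 65%, two-sided 5%, 5% loss, 1:1 allocation. Pooled-variance formula per arm, no continuity correction:

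n = [1.960·√(2·0.60·0.40) + z_power·√(0.55·0.45 + 0.65·0.35)]² / 0.10²

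- 80%: (1.3579 + 0.8416·0.6892)² / 0.01 = 375.6, so 376; 376/0.95 gives 396 per arm, 792 in total.
- 90%: (1.3579 + 1.2816·0.6892)² / 0.01 = 502.3, so 503; 503/0.95 gives 530 per arm, 1060 in total.

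Both stated totals reproduce exactly, and the calculation takes no credit for any covariate.

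**2. What adding size does.** Trials were simulated (2,000 per scenario) with 5% loss, marginal BCS fixed at 55% v 65%, and arms balanced within indication. Assumptions not in the documents: 45% indicated for mastectomy at baseline, an odds ratio of 2.5 per SD linking size to indication, and the effects in the table. Age, nodal status and centre were left out.

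| N | Indication OR | Size OR per SD within indication | Power: unadjusted | + indication | + indication + size |
|---|---|---|---|---|---|
| 792 | 7.4 | 1.5 | 0.840 | 0.900 | 0.908 |
| 792 | 7.4 | 2.0 | 0.836 | 0.908 | 0.921 |
| 792 | 7.4 | 3.0 | 0.837 | 0.910 | 0.942 |
| 792 | 20.1 | 1.5 | 0.857 | 0.952 | 0.954 |
| 792 | 20.1 | 2.0 | 0.862 | 0.962 | 0.971 |
| 792 | 20.1 | 3.0 | 0.874 | 0.962 | 0.980 |
| 1060 | 7.4 | 3.0 | 0.940 | 0.970 | 0.984 |

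Indication ORs of 7.4 and 20.1 are log-odds of 2 and 3. Size ORs of 1.5, 2.0 and 3.0 are about 0.4, 0.7 and 1.1 log-odds per SD. The gain from size is 0.2 to 3.2 points at N=792 and at most 1.4 points at N=1060. With no residual size effect (OR 1.0), power at N=792 and indication OR 7.4 was 0.890 without size and 0.888 with it, so the extra covariate costs nothing visible.

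**3. The same gain as information.** Large-sample calculations conditional on indication (log-odds 2 to 4; size 0.4 to 1.0 per SD) give about 2% to 14% more information on the treatment effect. With information ratio R and starting power P, new power ≈ Φ[√R·(1.960 + z_P) − 1.960].

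- P = 0.89, R = 1.14: √1.14·(1.960 + 1.227) − 1.960 = 1.442, power 0.925, a gain of 3.5 points.
- P = 0.89, R = 1.02: 1.258, power 0.896, a gain of 0.6 points.
- P = 0.95, R = 1.02: √1.02·(1.960 + 1.645) − 1.960 = 1.681, power 0.954, a gain of 0.4 points.

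At N=792, 2% to 14% is worth about 16 to 111 women (0.02·792 and 0.14·792). The top of the range needs the largest size effect and the weaker indication effect. With a low size–indication correlation (0.3) as well, that corner reaches about 15%, or 4 points.

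**4. Chance imbalance in size.** With 376 analysed per arm, the SE of the difference in mean size is √(2/376) = 0.073 SD, so 95% of trials lie within 1.96·0.073 = 0.143 SD. At 0.4 to 1.0 log-odds per SD that shifts the log odds by 0.06 to 0.14. The planned marginal log odds ratio is ln(0.65/0.35) − ln(0.55/0.45) = 0.42; the conditional one is larger. Balance on indication reduces the shift further.

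**The case against.** The strongest reply is that nothing here is wrong. A mixed logistic model that adjusts for the minimisation factors is standard for a minimised trial, and the most direct predictor of the operation, the one planned at baseline, is already in it. Only the part of size not captured by indication matters, and the documents do not quantify it. The operation also depends on surgeon and patient agreement (section 9.10), and ultrasound diameter is imperfect: section 9.9 calls for MRI where mammography and ultrasound sizes disagree. All of this stands, and it is why the gain is modest and its size uncertain.

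It could also be said that covariates belong in the SAP, which is not shown. That holds for naming the sensitivity-analysis factors, and their absence from the protocol is no fault. It does not cover the primary model: section 12.2 fixes that covariate set and places other prognostic factors outside it, so a SAP that follows the protocol will leave size out of the primary test.

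A reader might infer that the 80% design has little room without size. The documents do not support that: 792 follows from an unadjusted calculation, and under the assumptions above indication alone lifts power to about 0.89 or more. A reader might also infer that a chance size imbalance would bias the result. Under randomisation it is part of the sampling variation that the standard error already reflects.

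**Conclusion.** This is a worthwhile, nearly free improvement and not an error. That size is absent from the stated primary model, while being recorded at baseline in both arms, is certain from the text. The benefit is about 2% to 14% more information on the treatment effect, or roughly 0 to 3.5 points of power at N=792 and less at N=1060. Confidence in that magnitude is low, because it rests wholly on assumed effects of indication and of size within indication. If indication nearly determines the operation, the gain is about a point or less.

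The planned 80% and 90% power are met without the change, and the primary test keeps its type I error. The case does not extend to replacing the age bands with continuous age, for which no benefit has been shown.

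**What to change.** In section 12.2 and the SAP, name baseline ultrasound maximum tumour diameter (continuous, for example log mm) as a pre-specified fixed effect in the primary BCS model beside the stratification factors. Report the model with stratification factors and centre only as the sensitivity analysis.

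The cost is one sentence and no new data collection. Section 12.1 has the SAP finalised before the final data lock or any planned interim comparative analysis, and section 12.5 anticipates no formal interim comparison, so the change can still be made without sight of comparative results. One consequence to record: the treatment odds ratio will then be conditional on size as well as on the stratification factors, so it will not be numerically the same quantity as the odds ratio from the model without size.

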## 12.3 Sample Size Determination

We aim to recruit a maximum of 1060 patients (for 90% power, 530 per arm), with a minimum of 792 (for 80% power, 396 per arm) women from at least 30 NHS centres. UK-based registry data indicates that ~45% of women with tumours >2cm undergo mastectomy; based on discussions with patient representatives and confirmed at the NCRI Dragons Den, we consider a reduction of 10% (i.e. mastectomy rate reduced from 45% to 35% resulting in BCS rate increase from 55% to 65%) to be clinically meaningful to patients and lead to a change in clinical practice.

EndoNET\_Protocol\_V4.0\_21Aug2024

© Copyright: The University of Oxford and Oxford University Hospitals NHS Foundation Trust 2022 Page 63 of 84

The sample size of 1060, and 792, would allow us to detect this difference with 90% and 80% power respectively at a two-sided 5% significance level allowing for a cross-over and attrition at 15 months up to 5%.5% is based on loss to follow up experienced for the clinical endpoints in the iBra study.

80% power is considered to be sufficiently robust and in line with other similar and recent trials (104, 105). However, if recruitment to 1060 (for 90% power) seems achievable, given the observed recruitment trajectory, then the DSMC and TSC will be contacted to consider continuation of recruitment to 1060 patients.

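### For clinical secondary endpoints, Section 12.2 names unadjusted tests and makes covariate adjustment conditional, without saying which result is principal or using baseline tumour size; making the adjusted model principal costs almost nothing.

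*Protocol*

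**What the plan says.** Protocol Section 12.2 assigns methods by type of outcome.

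- **Continuous clinical endpoints:** "Continuous clinical endpoints will be compared using a two-group t-test", reported as a difference in means with a 95% interval.
- **Binary clinical endpoints:** a chi-squared test with a relative risk.
- **Ordinal clinical endpoints:** a chi-squared test for trend.

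These three statements carry no condition. The same paragraph then says that multilevel models adjusted for the stratification factors, in line with the primary analysis, "will be applied to secondary endpoints where it is both practical to do so" and where there are enough events. It defines neither condition. It also does not say whether the adjusted model replaces the simple test or stands beside it.

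Elsewhere in 12.2, adjustment is unconditional. The primary endpoint has a mixed logistic model with the clinical stratification factors and random centre. Quality of life has a mixed linear model with baseline score, stratification factors and random centre.

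Section 9.6 minimises allocation on age group, recruiting centre, baseline surgical indication and "Nodal status (N0 vs N1 or N2"). Sections 9.9.1 and 9.9.2 record the maximum ultrasound diameter at baseline in both arms. Section 6.2 lists tumour size at final histology (outcome 3) and rates of axillary surgery (outcome 10) as two-arm secondary outcomes.

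**The concern.** Minimisation makes the arms more alike on the chosen factors than simple randomisation would. If such a factor predicts the outcome, the true sampling variance of the treatment difference is close to the within-stratum variance. An unadjusted test still uses the total variance. Its interval is then too wide, its type I error falls below the nominal level and power is lost.

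Some clinical secondary endpoints are natural candidates. Section 9.10 makes the choice of axillary procedure depend on pre-operative nodal findings, and nodal status is a minimisation factor.

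Pathological tumour size raises a separate issue. The baseline ultrasound diameter is an obvious covariate, but the conditional adjusted model covers only the stratification factors, and tumour size is not one of them.

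What is at stake is precision on secondary endpoints, and a clear statement of which of two results is the trial's answer. Section 12.6 judges every two-arm outcome at p<0.05, so the ranking can decide how an endpoint is described.

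**Working it through.** **1. The plan's own figure.** Section 12.3 gives "BCS rate increase from 55% to 65"%, "with 90% and 80% power respectively" "at a two-sided 5% significance level", "allowing for a cross-over and attrition at 15 months up to 5"%. The pooled-variance formula is n = [1.96·√(2·0.60·0.40) + z·√(0.55·0.45 + 0.65·0.35)]² / 0.10².

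- 80% power (z = 0.842): 376 per arm; 752/0.95 = 792, as stated.
- 90% power (z = 1.282): 503 per arm; 1006/0.95 = 1059, against 1060 stated.

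The sample size is sound. No SD, event rate or power is stated for any secondary endpoint, so covariate strength must be assumed below.

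**2. Ignoring a balanced prognostic factor: general case.** Let R² be the share of outcome variance explained by the minimisation factors, with allocation treated as fully balanced on them. Take an effect of 0.204 SD with 376 per arm, which has 80% power by the usual t-test formula (1.96 + 0.842 = 2.802 standard errors). Put s = √(1−R²).

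- Ratio of adjusted to unadjusted interval width = s
- True type I error of the unadjusted test = 2·[1 − Φ(1.96/s)]
- Unadjusted power = Φ(0.842/s)
- Adjusted power = Φ(2.802/s − 1.96)

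| R² (assumed) | Width ratio | Type I error, unadjusted | Power, unadjusted | Power, adjusted |
|---|---|---|---|---|
| 0.05 | 0.975 | 4.4% | 80.6% | 82.0% |
| 0.10 | 0.949 | 3.9% | 81.3% | 84.0% |
| 0.20 | 0.894 | 2.8% | 82.7% | 87.9% |
| 0.30 | 0.837 | 1.9% | 84.3% | 91.8% |

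A simulation (4,000 runs, 752 patients, blocked allocation within 12 strata as a stand-in for minimisation) agrees. Unadjusted type I error was 4.0%, 3.6%, 2.7% and 1.6% in the four rows, against 4.7% to 5.0% adjusted. Power was 80.0 vs 81.6, 82.1 vs 84.3, 82.4 vs 87.7 and 84.1 vs 91.6%. Set against the nominal 80% instead, the gain is 2.0 points at R² 0.05 and 4.0 at R² 0.10. At 1060 patients the same figures apply to an effect of 0.177 SD.

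**3. Axillary clearance: illustration on the risk-difference scale.** All rates are assumed; 376 per arm; reduction of 7 points.

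*Strong case:* 25% node-positive, clearance 60% if node-positive and 5% if N0.
- Overall rate = 0.25·0.60 + 0.75·0.05 = 0.1875. Total variance = 0.1875·0.8125 = 0.1523.
- Within-stratum variance = 0.25·0.24 + 0.75·0.0475 = 0.0956. So R² = 1 − 0.0956/0.1523 = 0.37.
- Unadjusted SE too large by √(0.1523/0.0956) = 1.26. Type I error = 2·[1 − Φ(1.96·1.26)] = 1.3%.
- Power 74% unadjusted, 87% adjusted.

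*Milder case:* 20% node-positive, 50% and 5%. Variances 0.1204 and 0.0880, R² = 0.27, type I error 2.2%, power 83% vs 90%.

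These powers use control-rate variances in both arms. If the whole reduction falls in node-positive patients and each arm has its own variance, power is 80% vs 88% in the strong case and 91% vs 94% in the milder one.

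**4. Pathological tumour size.** Adjusting for baseline diameter multiplies the variance by 1 − ρ². At an assumed ρ of 0.4 this is 0.84 and at 0.6 it is 0.64: a cut of 16% to 36%. The unadjusted interval is wider by 1/√0.84 = 1.09 to 1/√0.64 = 1.25. Tumour size is not minimised on, so chance imbalance in it is part of the variance that the t-test correctly estimates. Omitting it costs precision and does not by itself push the error rate below 5%.

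**The case against.** The strongest reply is that 12.2 already provides for adjustment. Its closing sentence applies stratification-adjusted multilevel models wherever they are feasible. With 792 to 1060 patients that should rarely fail for continuous endpoints or for common binary ones. Section 12.2 also defers full detail to the SAP. Much of this stands: the loss arises only where the adjusted model is not used or not treated as the answer, and the SAP may settle the ranking. The deferral does not dispose of the point, because the protocol itself names the unadjusted tests without condition, and even its adjusted model leaves out baseline tumour size.

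A reader might infer more than the documents support.

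- *That secondary endpoints in general are unadjusted.* Quality of life is adjusted for baseline score, stratification factors and centre. Time-to-event outcomes have their own methods, including Cox and Fine and Gray models.
- *That type of breast surgery is affected.* That is the primary endpoint, already adjusted. The secondary breast outcomes are largely conditional on the operation received (re-excision after conservation, reconstruction after mastectomy), and minimisation does not guarantee balance in those subsets.
- *That the analysis may be picked after seeing results.* Section 9.7 requires the SAP before un-blinding and any comparative analysis, and Section 12.1 before the final data lock.
- *That the 26% excess in the SE is a property of this trial.* It rests on assumed rates and on the risk-difference scale. In a logistic model, adjustment raises power but generally does not narrow the interval for the log odds ratio.

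**Conclusion.** The point holds as a modest improvement to the stated method for clinical secondary endpoints; it is not an error that threatens the trial's conclusions.

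Where an endpoint is closely tied to a minimisation factor, the unadjusted test is conservative. The power lost is 2 to 4 points or less at R² up to 0.10 and about 5 to 8 points at R² of 0.20 to 0.30. For pathological tumour size, leaving out the baseline diameter forgoes a variance cut of 16% to 36% at correlations of 0.4 to 0.6.

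The documents give neither R² nor the correlation, and the calculation treats minimisation as achieving full balance. The random element in Section 9.6 would make the conservatism somewhat smaller. The fault produces no excess of false positives.

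**What to change.** In Section 12.2, and carried into the SAP:

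1. State that the model adjusted for the minimisation factors, with centre random, is the principal analysis for two-arm clinical secondary endpoints.
2. Add the baseline value as a covariate where one exists, in particular baseline ultrasound diameter for pathological tumour size.
3. Report binary effects on a stated marginal scale, such as a relative risk or risk difference standardised from the adjusted model, so that the measure already named in 12.2 is kept.
4. Keep the t-test and chi-squared tests only as the fallback when events are too few, with the threshold stated in advance.

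The cost is a few sentences and a little extra modelling. The minimisation factors and baseline ultrasound size are already collected, so no new data or patients are needed.
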